Procedure ^a	Arm A Bempegaldesleukin (NKTR-214) and Nivolumab Cycle = 3 Weeks (21 days)						Notes
	Cycle 1				Cycles 2-17		
	Day 1 (≤ 5 days post-randomization)	Day 3 (-1 day)	Day 5 (± 1 day)	Day 8 (± 1 day)	Day 1 (± 3 days)	Day 4 (± 1 day) (call or visit)	
Safety Assessments							
Targeted Physical Exam	X				X		Prior to dosing
Vital Signs and Weight	X				X		
 • Predose (bempegaldesleukin); includes blood pressure, pulse, respiratory rate, temperature, and weight (see Section 8.18) • Within 30 minutes after the end of nivolumab infusion; includes blood pressure, pulse, respiratory rate, and temperature (see Section 8.18)
Local Laboratory Tests	X				X		Within 24 hours (or as soon as locally feasible) prior to dosing to inform dosing decision; see Appendix 1
Local Pregnancy Test	X				X		Serum or urine pregnancy test (minimum sensitivity equivalent units 25 IU/L or equivalent units of HCG) is required within 24 hours prior to dosing in WOCBP to inform dosing decision; see Section 8.13.1
Central Laboratory Tests	X				X		Within 5 days prior to dosing; see Appendix 1
Performance Status	X				X		See Appendix 3
Adverse Events	Continuous assessment						Record at each visit
Concomitant Medications and Procedures	Continuous assessment						Record at each visit

Procedure ^a	Arm A Bempegaldesleukin (NKTR-214) and Nivolumab Cycle = 3 Weeks (21 days)						Notes
	Cycle 1				Cycles 2-17		
	Day 1 (≤ 5 days post-randomization)	Day 3 (-1 day)	Day 5 (± 1 day)	Day 8 (± 1 day)	Day 1 (± 3 days)	Day 4 (± 1 day) (call or visit)	
Pharmacokinetic and Exploratory Biomarker Samples							
PK and Immunogenicity Blood Samples	See Section 5.7 and Table 10 for details						
Biomarker Samples	See Section 5.8 XXXXXXXXXX						
CVA Biomarker Samples	See Section 5.8.2.4 for details						
Outcomes Research Assessments							
EORTC QLQ-C30	X				X		Predose (may be administered by telephone); performed for those ≥ 18 years of age at the time of informed consent, before any other study related procedures, and before the EQ-5D-5L; see Section 5.9 for additional details
EQ-5D-5L	X				X		Predose (may be administered by telephone); performed for those ≥ 18 years of age at the time of informed consent, before any other study-related procedures, and after the EORTC QLQ-C30; see Section 5.9 for additional details

Procedure ^a	Arm A Bempegaldesleukin (NKTR-214) and Nivolumab Cycle = 3 Weeks (21 days)						Notes
	Cycle 1				Cycles 2-17		

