5.3.4 Duration of Treatment

Patients will remain on treatment until:

- Disease recurrence (local, regional or distant), including new primary melanoma (except for MMIS Stage 0)
Note: Non-melanoma skin cancer does not require treatment discontinuation.
- Death
- Unacceptable toxicity
- Completion of up to approximately 1 year of study treatment (maximum of 17 cycles for Arm A and 13 cycles for Arm B)
- Symptomatic deterioration
- Investigator's decision to discontinue treatment
- Patient decision to discontinue treatment

- Patient withdraws consent for further treatment
- Patient is lost to follow-up
- Sponsor decides to terminate the study
- Meets any other discontinuation criteria listed in Section 5.12

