5.9 Health-Related Quality of Life (HRQoL)

Available therapies (e.g., interferon alpha) to treat patients with resected Stage IIIA (LN metastasis > 1 mm)/B/C/D and IV melanoma are associated with substantial toxicities and unclear clinical benefit. The evaluation of PROs in oncology clinical trials is becoming increasingly important to understand the benefits and risks of treatment from a patient perspective. However, PRO data from investigational trials in this population are lacking.

The EORTC QLQ-C30 will be used to assess changes from baseline in PROs during and after treatment. The GH/QoL and physical functioning subscales define secondary endpoints as they measure constructs deemed relevant to the population and have been prioritized by regulatory agencies and payers. The EQ-5D-5L will be used to assess general health status and capture data to calculate utilities for economic modeling.

Patients who are ≥ 18 years of age at the time of informed consent will be asked to complete the EORTC QLQ-C30 followed by the EQ-5D-5L before any other study-related procedures are performed as outlined in Section 1.2. Paper forms should be used when patients are in the clinic and phone script should be used when patients are in follow-up. Refer to Section 7.4 for additional information.

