## 5.2 Study Medications

Within 5 calendar days following randomization, the patient should receive the first dose of study treatment. Table 1 provides the timing of study drug administration.

Patients will be treated for approximately 1 year (maximum of 17 cycles for Arm A and 13 cycles for Arm B) or until disease recurrence, death, unacceptable toxicity, symptomatic deterioration, decision by investigator to discontinue treatment, decision by patient to discontinue treatment or withdraw consent from the study, patient is lost to follow-up, or decision by Sponsor to terminate the trial, whichever is earlier.

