## 6.0 STATISTICAL CONSIDERATIONS

### 6.1 General Considerations

Summary statistics for continuous variables will include the mean, standard deviation, median, minimum, and maximum. The mean and median will be presented to one decimal place beyond which the data were captured. The standard deviation will be presented to two decimal places beyond which the data were captured. The minimum and maximum will be presented to the precision with which the data were captured.

Categorical variables will be presented as frequency counts and percentages. A row or column denoted 'Missing' will be included in count tabulations where necessary to account for dropouts and missing values. Percentages will be rounded to 1 decimal place and the percent will be suppressed when the count is zero. The denominator will be the number of patients in the population of interest unless otherwise noted.

Data listings will be created to support each table and to present all data. Data listings will be presented by treatment group and patient number.

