### 6.11.2.5 Patient-Reported Outcomes (PROs)

The analysis of EORTC QLQ-C30 data will be performed in the Safety population. Scores for all EORTC QLQ-C30 items and subscales will be linearly transformed to a 0 to 100 metric where higher values indicate better functioning/well-being or lower symptom burden (see EORTC QLQ-C30 Scoring Manual). The primary domains of interest for the HRQoL analysis are GH/QoL and physical functioning of EORTC QLQ-C30.

Scores and post-baseline mean score changes and percent of subjects' HRQoL response status (e.g., improved, worsened, no change) compared to their baseline for the EORTC QLQ-C30 primary subscales will be summarized (e.g., mean with standard deviation and 95% CI, median, minimum, maximum) by treatment group and assessment time point. The clinically meaningful change for group-level analysis will be defined for each EORTC QLQ-30 domain as recommended by the literature ([Musoro, 2018](#)), specifically as 7 for GH/QoL and 5 for physical functioning. For individual-level analysis (i.e., percent of subjects who achieved the HRQoL change), the clinically meaningful change thresholds will be defined as 5 (-5) for improvement (deterioration) for both GH/QoL and physical functioning ([Cocks, 2015](#)).

The primary time point of interest will be Day 1 of Cycle 1 and Day 1 of Cycle 2-17 for Arm A, and Day 1 of Cycle 1 and Day 1 of Cycle 2-3 for Arm B.

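### The SAP's primary PRO time points are dosing visits only, and its default denominator makes the improved and worsened percentages both shrink as patients leave treatment

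*SAP*

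**What the plan says.** SAP 6.11.2.5 summarises QLQ-C30 scores, changes from baseline and improved/worsened status by arm at each assessment time point, in the Safety population. It then singles out certain visits: "The primary time point of interest will be Day 1 of Cycle 1 and Day 1 of Cycle 2-17 for Arm A". For the control arm the named range is much shorter and stops at the third cycle. Every visit named is a cycle Day 1. In Protocol Tables 2 and 3 the questionnaire on those days is tied to dosing: "Predose (may be administered by telephone); performed for those ≥ 18 years of age at the time of informed consent".

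Protocol 5.3.4 ends treatment at recurrence (in situ Stage 0 melanoma excepted) and at unacceptable toxicity. Protocol Table 4 nevertheless schedules the QLQ-C30 at Safety Follow-up Visits 1 and 2 and every 12 weeks in Survival Follow-up. The stated aim in Protocol 5.9 covers both phases: "The EORTC QLQ-C30 will be used to assess changes from baseline in PROs during and after treatment".

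On missing data, SAP 6.1 makes the population of interest the default denominator and adds a Missing row that "will be included in count tabulations where necessary to account for dropouts and missing values". SAP 6.4 gives rules for partial dates and plans no other imputation. Protocol 7.4, by contrast, records reasons for missing questionnaires so that a suitable imputation method can be chosen. Protocol 9.3 and 9.6.2 use an HRQoL population that requires a baseline and at least one later form. The SAP replaces it with the Safety population.

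**The concern.** Once a patient stops all study drug there is no further cycle Day 1, and so no further score at a time point the SAP calls primary. Later-cycle means then describe only patients still being dosed. Their former arm-mates may have completed forms in the same weeks, but nothing places those forms beside the cycle visits.

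The percentages have a separate problem. A Safety-population patient without a form stays in the denominator but can be counted neither as improved nor as worsened. Both percentages therefore drift down as patients leave, and a falling percentage worsened could be read as better tolerability. The same default also counts treated adolescents, who are never given the form.

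What is at stake is how a reader interprets a secondary endpoint that will still be reported. No hypothesis test is involved.

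**Working it through.** **Plan's own figure.** The documents give no sample size, power or effect for the PRO analysis, so there is no PRO figure to reproduce. I size the gap with the RFS planning model in Protocol 9.2 and SAP 6.2. As a check on that model: 950 patients, 22.5 months of accrual with a 7-month ramp-up taken as linear, 5% annual dropout and HR 0.7 give 321, 361 and 400 events at 42, 54 and 68 months. The plan states 320, 360 and 400.

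**Calendar.** SAP 5.2 allows a "maximum of 17 cycles for Arm A and 13 cycles for Arm B".
- Arm A Cycle 17 Day 1: (17 − 1) × 3 = week 48.
- Arm B Cycle 13 Day 1: (13 − 1) × 4 = week 48.
- Arm B Cycle 3 Day 1, its last primary time point as written: (3 − 1) × 4 = week 8.

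**One patient.** Suppose an Arm A patient's last dose is Cycle 5 Day 1, at week (5 − 1) × 3 = 12. Cycles 6 to 17 (weeks 15 to 48) are 12 primary time points with no score. Table 4 forms fall at about:
- week 12 + 30/7 = 16 (Safety Follow-up 1)
- week 12 + 100/7 = 26 (Safety Follow-up 2)
- weeks 38 and 50 (Survival Follow-up)

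**Share removed by recurrence or death.** Assume dosing stops at the RFS event.
- Control hazard, months 0 to 3: −ln(0.90)/3 = 0.0351 per month. Months 3 to 12: −ln(0.705/0.90)/9 = 0.02713 per month.
- Week 48 = 48 × 7/30.4375 = 11.04 months. Control RFS = 0.90 × exp(−0.02713 × 8.04) = 0.724. Arm A at HR 0.7 = 0.724^0.7 = 0.797.
- Arm A removed by week 48: 1 − 0.797 = 20%, or 1 − 0.724 = 28% if HR = 1.
- Week 24 (5.52 months): control 0.841, Arm A 0.885, so 12% of Arm A removed (16% if HR = 1).
- Arm B at week 8 (1.84 months): exp(−0.0351 × 1.84) = 0.937, so 6% removed.

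**Adding toxicity stops (assumption).** The documents give no stop rate for this setting. With an independent stop rate of 0%, 10%, 17.1% or 25%, the share of Arm A still dosed at week 48 is 0.797 × (1 − rate) = 80%, 72%, 66% or 60%. If HR = 1 it is 72%, 65%, 60% or 54%. The 17.1% is 7 of 41 in the earlier first-line metastatic melanoma cohort (Protocol 2.1.3.2.3).

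**Effect of the denominator.** Displayed percentage = percentage among patients with a form × share with a form. If every dosed patient completes the form, recurrence or death alone scales both percentages by 0.797 at week 48 in Arm A (0.724 if HR = 1).

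**Termination.** SAP 5.1 reports about 774 patients enrolled at the announcement. If accrual followed plan, 50 × 7/2 = 175 were in by month 7, and 774 was reached at month 7 + (774 − 175)/50 = 18.98. Those randomized at least 11.04 months earlier number 175 + 50 × (7.94 − 7) = 222, or 222/774 = 29%. About 71% could not have reached week 48 by that date, whatever their outcome. The data cutoff is not given.

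**The case against.** The best defence is that this is a descriptive summary in a terminated study, with all between-arm comparisons cancelled. An on-treatment summary is a legitimate target. A primary time point only sets emphasis, a Missing row is shown, and all data are to be listed. Much late-cycle missingness will come from termination, which is unrelated to outcome. Follow-up forms are sparse, often taken by telephone, and may follow subsequent therapy.

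Most of that stands and limits the point. It does not supply a common time scale, and it does not justify percentages whose denominator includes patients who could not contribute to the numerator.

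A reader might infer more than the documents support:
- **Follow-up questionnaires are discarded.** They are not. Summary at each assessment time point can include them.
- **Patients who stopped have no scoring rule.** They do. SAP 6.1 and 6.4 leave the score missing and display it as missing.
- **A third of each arm is unscored at the last cycles.** As written, Arm B ends at week 8, where planning RFS is 93.7%. In Arm A the figure needs the 17.1% rate, which comes from a metastatic cohort, is added as if independent, and ignores that Protocol 5.12.1 lets some Arm A patients continue one drug and keep their cycle visits.
- **Bias is worse in the arm with more toxicity.** With 17.1% in Arm A and an assumed 10% in Arm B, the week-48 losses are 1 − 0.797 × 0.829 = 34% and 1 − 0.724 × 0.90 = 35%: no difference.
- **Mean change is overstated by 1.7 to 5.1 points** (0.34 × 5 to 0.34 × 15, against thresholds of 7 and 5). The gap of 5 to 15 points is assumed, and patients who stop for toxicity may improve once off drug.

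**Conclusion.** The point holds as one of structure and presentation. The primary PRO time points exist only while a patient is being dosed, the follow-up forms are not aligned with them, and the default denominator pulls both the improved and the worsened percentages down as patients leave. An Arm A patient who stops only one drug is not affected.

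On the planning model about 20% of Arm A would be lost to recurrence or death by week 48 (28% if HR = 1), assuming dosing stops at the event. Toxicity would add an unknown amount. Early termination adds administrative missingness that may well dominate the late cycles. The size and direction of any bias in the mean are unknown, and no difference in bias between arms is shown. This is selection in displayed summaries, not a testing error.

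The Arm B range ending at Cycle 3 conflicts with Protocol Table 3, which schedules the form for Cycles 2 to 13. As written, the primary window is 48 weeks in one arm and 8 in the other.

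**What to change.** 1. Keep the by-cycle table and label it on-treatment.
2. Compute improved and worsened percentages on patients with both a baseline form and a form at that time, with n shown.
3. Add one descriptive table of change from baseline at fixed times from randomization, for example weeks 12, 24, 36 and 48 where data allow, using the nearest form from any visit. At each time give counts by arm: on treatment, off treatment with a form, off treatment without a form, dead, and not yet reached because of termination.
4. Reconcile the Arm B cycle range in SAP 6.11.2.5 with Protocol Table 3.

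The cost is SAP wording and one table from forms already collected. No new data are needed and no sample-size figure changes. The downside is that follow-up forms are sparser, mix clinic and telephone completion, and may follow subsequent therapy. After termination the week-48 column may be thin, and the counts will show that.

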ECG	X	Within 14 days prior to randomization (see Section 8.19)
Echocardiogram or MUGA	X	Within 60 days prior to randomization (see Section 8.20)
EORTC QLQ-C30	X	Within 14 days prior to randomization (see Section 7.4.1) Performed for those ≥ 18 years of age at the time of informed consent and before any other study-related procedures
Randomization		
Randomization in IRT	X	Patient should be dosed within 5 calendar days following randomization

CT = computed tomography; ECG = electrocardiogram; EORTC QLQ-C30 = 30-item European Organisation for Research and Treatment of Cancer Core Quality of Life Questionnaire; HCG = human chorionic gonadotropin; IRT = Interactive Response Technology; MRI = magnetic resonance imaging; MUGA = multigated acquisition; PD-L1 = programmed cell death ligand 1; WOCBP = women of childbearing potential.

Table 2: On-Treatment Schedule of Events for Arm A

Procedure ^a	Arm A Bempegaldesleukin (NKTR-214) and Nivolumab Cycle = 3 Weeks (21 days)						Notes
	Cycle 1				Cycles 2-17		
	Day 1 (≤ 5 days post-randomization)	Day 3 (-1 day)	Day 5 (± 1 day)	Day 8 (± 1 day)	Day 1 (± 3 days)	Day 4 (± 1 day) (call or visit)	
Study Drug and Hydration Follow-up							
Study Drug Administration	X				X		Dispense and administer study drugs following all predose assessments. Following first dose, subsequent doses of study drug may be administered no less than 18 days after prior dose of study drug. After the bempegaldesleukin infusion is administered, flush the IV line with an appropriate amount of diluent. If needed, flush the IV line with an appropriate amount of diluent after the nivolumab infusion. Refer to Section 5.3.2 and Pharmacy Manual for details.
IV Hydration and Review Oral Hydration Guidelines with Patient	X				X		Applicable only when bempegaldesleukin is administered. May be withheld if deemed in the best interest of the patient by the Investigator. Refer to Section 5.3.3.2 for further details.
Oral Hydration Follow-up		X ¹				X ^{1,2}	X ¹ = For Cycle 1 and Cycle 2, site personnel must contact the patient (by telephone or clinic visit) at least once between Days 3 and 5, inclusive, to remind the patient of the oral hydration guidelines, to assess for any symptomatology and compliance with hydration guidelines, and document the results of the discussion (Section 5.3.3.2). X ² = For Cycles 3 to 17, oral hydration follow-up should be conducted as clinically indicated between Days 3 and 5, inclusive.

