Note: If scheduled visits or assessments coincide with a weekend or holiday, schedule at the next feasible date. Please contact the Medical Monitor to discuss any concerns about study visits or assessments that may fall out of the protocol-specified window because of unforeseen delays or other patient-specific circumstances. All out of window visits and procedures will incur a protocol deviation.

Table 3: On-Treatment Schedule of Events for Arm B

Procedure ^a	Arm B Nivolumab Cycle = 4 Weeks (28 days)			Notes
	Cycle 1		Cycles 2-13	
	Day 1 (≤ 5 days post- randomization)	Day 8 (± 1 day)	Day 1 (± 3 days)	
Study Drug				
Study Drug Administration	X		X	Dispense and administer study drugs following all predose assessments. Following first dose, subsequent doses of study drug may be administered no less than 25 days after prior dose of study drug. If needed, flush the IV line with an appropriate amount of diluent after the nivolumab infusion. Refer to Section 5.3.2 and Pharmacy Manual for details.
Safety Assessments				
Targeted Physical Exam	X		X	Prior to dosing
Vital Signs and Weight	X		X	
 Predose; includes blood pressure, pulse, respiratory rate, temperature, and weight (see Section 8.18) Within 30 minutes after the end of nivolumab infusion; includes blood pressure, pulse, respiratory rate, and temperature (see Section 8.18)
Local Laboratory Tests	X		X	Within 24 hours (or as soon as locally feasible) prior to dosing to inform dosing decision; see Appendix 1
Local Pregnancy Test	X		X	Serum or urine pregnancy test (minimum sensitivity equivalent units 25 IU/L or equivalent units of HCG) is required within 24 hours prior to dosing in WOCBP to inform dosing decision; see Section 8.13.1
Central Laboratory Tests	X		X	Within 5 days prior to dosing; see Appendix 1
Performance Status	X		X	See Appendix 3

Procedure ^a	Arm B Nivolumab Cycle = 4 Weeks (28 days)			Notes
	Cycle 1		Cycles 2-13	
	Day 1 (≤ 5 days post-randomization)	Day 8 (± 1 day)	Day 1 (± 3 days)	
Adverse Events	Continuous assessment			Record at each visit
Concomitant Medications and Procedures	Continuous assessment			Record at each visit
Pharmacokinetic [REDACTED] Biomarker Samples				
PK and Immunogenicity Blood Samples	See Section 5.7 and Table 10 for details			
Biomarker Samples	See Section 5.8 and Table 11 for details			
CVA biomarker samples	See Section 5.8.2.4 for details			
Outcomes Research Assessments				

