EORTC QLQ-C30	X		X	Predose (may be administered by telephone); performed for those ≥ 18 years of age at the time of informed consent, before any other study related procedures, and before the EQ-5D-5L; see Section 5.9 for additional details
EQ-5D-5L	X		X	Predose (may be administered by telephone); performed for those ≥ 18 years of age at the time of informed consent, before any other study-related procedures, and after the EORTC QLQ-C30; see Section 5.9 for additional details

Procedure ^a	Arm B Nivolumab Cycle = 4 Weeks (28 days)			Notes
	Cycle 1		Cycles 2-13	
	Day 1 (≤ 5 days post-randomization)	Day 8 (± 1 day)	Day 1 (± 3 days)	
Efficacy Assessments				
Imaging Assessment	Every 12 weeks (± 7 days) for up to 24 months from the date of randomization and then every 6 months (± 4 weeks) for up to 5 years (60 months) from the date of randomization; see Section 7.3 for additional details: 
 • CT (contrast-enhanced preferred, unless contraindicated) of chest and CT or MRI (contrast-enhanced preferred, unless contraindicated) of abdomen, pelvis, and all other known sites of resected disease • Ultrasound of sentinel-node basin • Brain imaging for patients with baseline history of treated brain lesions: Brain MRI (without and with contrast; head CT with contrast allowed if patient develops contraindication for MRI) on the same schedule as other imaging • Brain imaging for patients without baseline history of brain metastases: Brain MRI (without and with contrast; head CT with contrast allowed if MRI contraindicated) annually from the date of randomization and as clinically indicated Notes: 
 - Imaging assessment schedule is relative to the date of randomization and will be maintained regardless of dose delays or study drug discontinuation. - Use same imaging method as was used at Screening/Baseline - Continue imaging assessments until investigator-assessed and BICR-confirmed distant recurrence as defined in Section 7.1. 			

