To evaluate PD-L1 expression as a predictive biomarker, a Cox proportional hazards model will be used to test the interaction between PD-L1 expression ($\geq 1\%$ vs $< 1\%$) and treatment arm for the RFS endpoints. Additionally, RFS will be analyzed within each PD-L1 expression subgroup ($\geq 1\%$ vs $< 1\%$) including log-rank tests and hazard ratios with corresponding CIs. The Kaplan-Meier method will be used to further summarize RFS, including Kaplan-Meier curves, medians and 95% CIs, and RFS rates in each subgroup at 6, 12, 18, 24, and every 12 months thereafter with 95% CIs. The analyses will be descriptive.

The analysis of EORTC QLQ-C30 data will be performed in the HRQoL population (defined in Section 9.3). Scores for all EORTC QLQ-C30 items and subscales will be linearly transformed to a 0 to 100 metric where higher values indicate better functioning/well-being or lower symptom burden (see EORTC QLQ-C30 Scoring Manual). The primary domains of interest for the HRQoL analysis are GH/QoL and physical functioning of EORTC QLQ-C30.

Scores and post-baseline mean score changes and percent of subjects' HRQoL response status (e.g., improved, worsened, no change) compared to their baseline for the EORTC QLQ-C30 primary subscales will be summarized (e.g., mean with standard deviation and 95% CI, median, minimum, maximum) by treatment group and assessment time point. The clinically meaningful change for group-level analysis will be defined for each EORTC QLQ-30 domain as recommended by the literature (Musoro, 2018), specifically as 7 for GH/QoL and 5 for physical functioning. For individual-level analysis (i.e., percent of subjects who achieved the HRQoL change), the clinically meaningful change thresholds will be defined as 5 (-5) for improvement (deterioration) for both GH/QoL and physical functioning (Cocks, 2015).

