### 3.0 STUDY OBJECTIVES

This section shows planned primary, secondary and exploratory objectives from the study protocol. However, due to early study termination, no blinded independent central review (BICR) data is available, thus the analyses for the primary endpoint of recurrence-free survival (RFS) by BICR, and the analyses for the secondary endpoints of distant metastasis-free survival (DMFS) by BICR and association between PD-L1 expression status and RFS by BICR will not be performed in the final study CSR. Descriptive analyses for the secondary endpoint of RFS by investigator and other secondary endpoints will be done based on available data. All comparative analyses comparing Arm B vs Arm A will not be conducted.

Due to early study termination, analyses and parameter calculations specified in the protocol for pharmacokinetic (PK), immunogenicity, biomarker (except PD-L1), clinical laboratory are no longer planned to be conducted. Other analyses no longer planned to be performed are vital signs, physical examination, electrocardiogram (ECG), concomitant medications, other safety observations for bempegaldesleukin, prior medications, prior therapy (cancer-related radiotherapy, systemic therapy), prior melanoma-related surgery, medical history, post-study cancer therapy and important protocol deviations. The analyses for all exploratory endpoints will not be performed.

[figure not shown]

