#### 3.2 Secondary Objectives

The secondary objectives are:

- To compare the overall survival (OS) of bempegaldesleukin (NKTR-214) plus nivolumab versus nivolumab monotherapy in patients with completely resected Stage IIIA (LN metastasis > 1 mm), Stage IIIB/C/D, or Stage IV NED melanoma
- To evaluate DMFS by BICR and by investigator in patients who have Stage IIIA (LN metastasis > 1 mm) or IIIB/C/D melanoma at study entry
- To evaluate time to disease progression after the next line of treatment for study patients following discontinuation of bempegaldesleukin (NKTR-214) plus nivolumab versus nivolumab monotherapy

- To assess the overall safety and tolerability of bempedaldesleukin (NKTR-214) plus nivolumab versus nivolumab monotherapy in study patients
  - To describe changes in patient-reported outcomes (PROs) as assessed by the global health/quality of life (GH/QoL) and physical functioning subscales of the 30-item European Organisation for Research and Treatment of Cancer Core Quality of Life Questionnaire (EORTC QLQ-C30)
  - To evaluate the association between PD-L1 expression status and RFS by BICR
  - To assess the efficacy, as measured by RFS by investigator, of bempedaldesleukin (NKTR-214) plus Nivolumab versus Nivolumab monotherapy in patients with completely resected Stage IIIA (LN metastasis > 1 mm), Stage IIIB/C/D, or Stage IV NED melanoma
- 

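### The SAP's primary PRO time points stop at Cycle 3 in Arm B, although the QLQ-C30 is scheduled there through Cycle 13 and Arm A keeps its full range to Cycle 17.

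*SAP*

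**What the plan says.** SAP 6.11.2.5 ends with a sentence naming the PRO time points of primary interest. For Arm A these are Day 1 of Cycle 1 and Day 1 of Cycles 2 to 17. For Arm B they are "Day 1 of Cycle 1 and Day 1 of Cycle 2-3 for Arm B".

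The other relevant places are:

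- **Protocol 1.2, Table 2 (Arm A):** columns for Cycle 1 and Cycles 2 to 17, with the QLQ-C30 marked on Day 1 in both.
- **Protocol 1.2, Table 3 (Arm B):** columns for Cycle 1 and Cycles 2 to 13, with the QLQ-C30 marked on Day 1 in both.
- **SAP 5.2:** a "maximum of 17 cycles for Arm A and 13 cycles for Arm B". Protocol 5.3 gives the same maxima.
- **SAP 3.2:** one secondary objective is "To describe changes in patient-reported outcomes (PROs) as assessed by the global health/quality of life (GH/QoL) and physical functioning subscales" of the QLQ-C30.
- **SAP 3.0, on early termination:** "Descriptive analyses for the secondary endpoint of RFS by investigator and other secondary endpoints will be done based on available data". The analyses dropped are listed item by item, and the PRO analysis is not among them.
- **Protocol 9.6.2:** QLQ-C30 scores and changes are to be summarised "by treatment group and assessment time point", with no cycle limit. SAP 6.11.2.5 repeats this.

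**The concern.** The two arms are treated differently without a stated reason. Arm A's range reproduces its visit schedule in full. Arm B's stops at the third of 13 cycles and differs from the scheduled range by a single digit.

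Early termination does not account for this. It affected both arms of a 1:1 randomised trial, yet Arm A keeps Cycle 17. The same SAP still plans 12-month rates by treatment arm for OS, DMFS by investigator, PFS2 and RFS by investigator. SAP Table 4 defines Arm B exposure with no Cycle 3 limit. Nothing suggests that Arm B follow-up was regarded as ending after about two months.

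At stake is the description of a retained secondary objective. A programmer who follows the sentence literally would present about 11 months of Arm A and about 2 months of Arm B as the time points of primary interest. A reader of the study report would have no explanation for the difference.

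**Working it through.** This is schedule arithmetic. No sample size, power or alpha is involved.

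**Inputs**

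- Cycle length: 21 days in Arm A (Protocol Table 2) and 28 days in Arm B (Protocol Table 3).
- Maximum cycles: 17 in Arm A and 13 in Arm B (SAP 5.2, Protocol 5.3).
- QLQ-C30 on Day 1 of every cycle in both arms (Protocol Tables 2 and 3).
- Primary PRO time points: Cycles 1 to 17 in Arm A and Cycles 1 to 3 in Arm B (SAP 6.11.2.5).

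**Check against the plan's own figure.** Treatment length is cycles × cycle length:

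- Arm A: 17 × 3 = 51 weeks
- Arm B: 13 × 4 = 52 weeks

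Both agree with the stated duration of approximately 1 year, so 17 and 13 are the matching full ranges for the two arms.

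**Nominal timing.** Counted from first dose, Day 1 of cycle k falls at 3(k − 1) weeks in Arm A and 4(k − 1) weeks in Arm B:

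- Arm A, Cycle 17: 3 × 16 = week 48
- Arm B, Cycle 3: 4 × 2 = week 8
- Arm B, Cycle 4: 4 × 3 = week 12
- Arm B, Cycle 13: 4 × 12 = week 48

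**Scheduled Day 1 visits designated primary**

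| | Arm A | Arm B as written | Arm B if Cycles 2 to 13 |
|---|---|---|---|
| All Day 1 visits | 17 of 17 | 3 of 13 (23%) | 13 of 13 |
| After Cycle 1 | 16 of 16 | 2 of 12 (17%) | 12 of 12 |
| Last nominal week | 48 | 8 | 48 |

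In Arm B, 10 of 13 scheduled visits (77%) fall outside the designation, or 10 of 12 (83%) after Cycle 1. These are Cycles 4 to 13, nominal weeks 12 to 48.

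**Nominal weeks common to both arms.** Arm A visits fall at multiples of 3 weeks and Arm B visits at multiples of 4. Over the full schedules they coincide at weeks 0, 12, 24, 36 and 48. With Arm B stopped at week 8, only week 0 is common.

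**The case against.** The best case against the point concerns its consequence. The instruction in SAP 6.11.2.5 to summarise scores, changes and response status by arm and time point has no cycle limit, and SAP 6.1 requires listings that present all data. On that reading Arm B Cycles 4 to 13 are still summarised and listed. The SAP attaches no test, model, restricted table or imputation rule to the primary time points. SAP 6.11 cancels between-arm comparisons. The 77% and 83% are therefore shares of scheduled visits without a label. They do not measure missing data or bias. SAP 5.1 also says the data are limited by early termination.

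A second argument is that a collection schedule does not dictate which visits an analysis plan calls primary. The SAP leaves the safety and survival follow-up questionnaires in Protocol Table 4 out of the designation for both arms, and Protocol 9.6.2 names no primary PRO time points that the SAP could contradict.

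Most of this stands, and it keeps the point small: no result is lost and no inference changes. It does not explain why one arm's on-treatment range is complete and the other's stops at Cycle 3. Leaving out follow-up visits is symmetric between arms, but the Cycle 3 stop is not. The objection also leaves the designation itself wrong as written, in an operative analysis section for an objective that will be reported.

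**Conclusion.** The point holds. SAP 6.11.2.5 designates 3 of 13 scheduled on-treatment Day 1 visits as primary in Arm B, to nominal week 8, and 17 of 17 in Arm A, to nominal week 48. Neither document gives a reason for the difference.

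That this is a misprint for Cycles 2 to 13 is an inference. It rests on the exact match of Arm A to its schedule, the 13-cycle maximum in the SAP itself, and the absence of any PRO cut-off in the termination text. The documents do not confirm it. The counts are of scheduled visits at nominal weeks. The number of questionnaires completed is not stated, and no claim is made about actual visit windows.

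The effect is confined to which Arm B visits are labelled primary in a descriptive analysis. It should be corrected because the objective is still to be reported.

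**What to change.** In SAP 6.11.2.5, change the Arm B range so that it covers Day 1 of Cycle 1 and Day 1 of Cycles 2 to 13. If the shorter range was intended, add a sentence saying why Arm B alone stops at Cycle 3.

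The cost is one digit or one sentence. No new assessment is needed, because Protocol Table 3 already schedules these visits.
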